## 5 STUDY INTERVENTION(S) OR EXPERIMENTAL MANIPULATION(S)

### 5.1 STUDY INTERVENTION(S) OR EXPERIMENTAL MANIPULATION(S) ADMINISTRATION

#### 5.1.1 ADMINISTRATION AND/OR DOSING

All PN+SPI intervention sessions will be conducted by social work navigators who will be hired by our clinical partner, Family Health Centers of San Diego, based on their familiarity with the intended audience, young SGMs. The first intervention session will be held immediately following study enrollment (i.e. during the baseline assessment). While the COVID-19 outbreak is on-going, this session will be conducted online via Zoom (a secured video calling platform with audio and video capabilities) instead of in-person to ensure proper care and safety of participants and study staff. All participants will receive the SPI during this first intervention session. Additionally, the patient navigator will assess barriers to accessing mental health care services and SGM social support services at this time.

Given that PN interventions are flexible by design in order to address participants' unique barriers to care, the PN+SPI intervention will not be administered according to any predetermined frequency or schedule. At minimum, the patient navigator will contact participants using their preferred method (e.g., over the phone) one time per week for the next seven weeks and then monthly for the remainder of the intervention period. However, some participants may require additional assistance from the patient navigator. Therefore, the patient navigator will deliver the intervention modules based on the particular concerns and needs of each participant, repeating modules as needed. As a result, there is no predetermined number of intervention sessions constituting a complete or "full-dose" intervention. We will monitor the dose of patient navigation (as measured by the quantitative variables of frequency of service delivery, amount of time spent with participants, and actions taken) by utilizing a PN encounter form. Lastly, participants will not interact with other participants or with a shared interventionist throughout the duration of the study.

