Study Population:	The case series will consist of up to 10 sexual and gender minority participants, aged 15-29, located in San Diego. The open trial will consist of 30 sexual and gender minority participants, aged 15-29, located in San Diego. The participants in both the case series and open trial are generally physically healthy but are currently experiencing suicidal ideation and have attempted suicide in the past.
Description of Sites/Facilities Enrolling Participants:	San Diego State University (SDSU) is the only site enrolling participants for both the case series and open trial.
Description of Study Intervention/Experimental Manipulation:	The study intervention integrates a brief (30 minute), empirically supported, single-session suicide prevention intervention (Safety Planning Intervention; SPI) with patient navigation (PN) services (PN+SPI). Intervention dose will vary by participant based on their individual needs. All PN+SPI intervention sessions will be administered individually. The first PN+SPI intervention session will occur either remotely or in-person. After the initial session, the remaining intervention sessions will occur according to the participant's preferred contact method (e.g., Zoom-based, over the phone).
Study Duration:	The estimated time from when the study opens to enrollment until completion of data collection is five months for the case series and fifteen months for the open trial.
Participant Duration:	In the case series, it will take three months for each individual participant to complete all study related tasks. In the open trial, it will take six months for each individual participant to complete all study-related tasks.

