The SPI is a 30-minute behavioral intervention to reduce suicide attempts by providing individuals with specific actionable behaviors they can engage in to reduce the likelihood of acting on suicidal urges, including: 1) identification of suicidality warning signs; 2) implementing personal coping strategies; 3) connecting with mental health professionals; 4) connecting with friends and/or family for support; 5) connecting with mental health professionals; and 6) reducing access to means of completing suicide. In a recent trial of the SPI, 1,640 patients with suicide risk received either the SPI or usual care and were followed for six months. Results indicated that participants who received the SPI significantly reduced suicidal behaviors compared to the comparison condition, with 45% fewer suicide attempts noted among the SPI participants compared to usual care.

The PN+SPI intervention is a multi-level intervention and will target several hypothesized mechanistic targets that theoretically underlie the impact of the PN+SPI on reduction in suicide attempts. One proposed target of the intervention is decreased thwarted belongingness (e.g. through interactions with the PN and connection with SGM-specific support groups). For example, in a recent meta-analysis of over 100 unique samples, thwarted belongingness was significantly associated with increased suicide risk ( $r = .33$ ). Additionally, among a sample of sexual minority and heterosexuals, the association between thwarted belongingness and suicide ideation was

stronger amongst SMs and SM participants with a history of suicide attempts reported substantially higher thwarted belongingness compared to SMs with no history of suicide attempts ( $d = .54$ ). SMs also report greater thwarted belongingness compared to their heterosexual peers ( $d$  range from .80 to .97). Related, thwarted belongingness has also been found to predict suicide attempts among gender minority youth (Odds Ration [OR] = 2.88).

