The patient navigation procedures will facilitate receipt of high-quality mental health care. The intervention will be implemented by a social work navigator who will be under the supervision of [name], a licensed clinical psychologist, and [name], a trained clinical psychologist. The assessment of intervention fidelity will also help to ensure that clinical protocols are being implemented as designed. Study navigators will also have ready access to the Principal Investigators, as well as their direct supervisor at the Family Health Centers of San Diego (FHCSD). In all cases, participant health and safety have priority over study protocol. Study procedures do not preclude participant referral for additional care and treatment.

Other potential risks include the possibility that confidentiality could be breached, as well as possible discomfort about treatment sessions and assessments being audio-recorded for supervision and treatment adherence checks. Participants will be advised that they can refuse to be audio-recorded. All data will be kept confidential, under lock-and-key, or electronically and password protected, accessible only to trained study staff. Participants' data will be identified by an ID number only, and a link between names and ID numbers will be kept separately under lock-and-key or electronically and password protected, again accessible only to trained study staff. All digital audio recordings of sessions will be uploaded to the study computer immediately post-session and the file deleted from the digital recorder. Computer files will be secured by password and will be accessed only by authorized study personnel. These procedures will be implemented to provide study participants with the assurance of confidentiality around very sensitive and personal information.

The purpose of the study is to develop and test a PN+SPI prevention program for SGM youth and young adults. Despite the vulnerability of these populations to suicide, there are currently no known suicide prevention programs for them. Results from the study will provide important information which could reduce the mortality of these populations.

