### 3 STUDY DESIGN

#### 3.1 OVERALL DESIGN

There are no hypotheses associated with the case series given that the purpose of the case series is to obtain feedback on study procedures and the PN+SPI intervention. For the open trial, we hypothesize that PN+SPI participants will display decreases in thwarted belongingness and increases in suicide-related coping skills (the hypothesized mechanistic targets of the intervention). We will also assess the feasibility and acceptability of the PN+SPI intervention during the open trial.

As stated, the case series (up to 10 participants) will be conducted to refine study procedures and the PN+SPI intervention. In terms of trial type, the open phase trial is a within-subjects trial. All participants in the case series and open trial will be assigned to the PN+SPI intervention. Therefore, no randomization or control group will be used.

The case series (N = 10) is a one group, one arm study. Participants in the case series will receive up to three months of the patient navigation plus safety planning intervention, at which

point they will complete a three-month follow-up assessment. The open phase trial (N = 30) is also a one group, one arm study and will follow the same approach; however, there will be both a three-month and six-month follow-up assessment, and intervention services will be provided for six months. The R61 phase (e.g., case series and open trial) precedes a potential R33 phase, in which the theoretical targets of the intervention will be further tested in a RCT.

The study intervention includes patient navigation (PN) for SGM youth/emerging adults designed to target mechanisms (i.e. decreasing thwarted belongingness and increasing suicide-related coping skills) that theoretically underlie suicide. The study intervention integrates a single-session, empirically supported, suicide prevention intervention (Safety Planning Intervention; SPI) with PN services (PN+SPI).

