#### 4.4 STRATEGIES FOR RECRUITMENT AND RETENTION

We do not have an anticipated number to be screened in order to reach the target enrollment size for the case series. We will use data collected as part of the case series to help us determine the anticipated number to be screened in order to reach the target enrollment size in the open trial.

The anticipated accrual rate over the course of the case series is five participants per month over two months (total  $N = 10$ ). The anticipated accrual rate over the course of the open trial is five participants per month over six months (total  $N = 30$ ).

A broad recruitment strategy will be used to recruit diverse participants within the greater San Diego area via a variety of methods, including FHCSD outreach programs, support groups, flyering local LGBT community centers, gay-identified/friendly coffee shops, gyms, and bars. We will also utilize online recruitment methods, including targeted ads through Facebook/Instagram, and use of geolocation social networking mobile applications tailored to SGM (e.g. Grindr, Scruff, Jacked). Finally, we will also recruit from the BISH Lab registry, a database of diverse SGM community members who are willing to be contacted for research projects. This multi-method approach has been in our current and previous studies sampling SGM, is a frequently used method among researchers studying SGM and is cost-effective. We already have developed several recruitment flyers and ads for other studies that can be modified to recruit participants that reflect the ethnic and racial diversity of San Diego County. We have also budgeted funding for the expenses related to study recruitment to help ensure our success.

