Intervention fidelity will be assessed via audio-recordings and observation conducted by the study project director. Audio-recordings, considered the gold standard in treatment fidelity, will be evaluated by the trained project director who will code the recordings using a checklist to track whether the interventionists delivered PN+SPI according to the manual. Using an approach developed by the PNRP, patient navigators will record process data related to the PN services provided, including: 1) number of encounters, 2) length of time of each encounter; 3) barriers experienced by patients; and 4) actions taken to reduce barriers. Patient navigators will keep copies of the participants' safety plans and the SPI suicide risk curve. The patient navigators will also be asked to keep detailed qualitative notes regarding telephone, text, and in-person encounters with participants, including participants' progress in obtaining mental health services, successes in implementing the PN intervention, and challenges in implementing the PN intervention. A Research Program Manager at FHCSD will provide day-to-day supervision of the patient navigators and will meet with the navigators weekly and document successes and challenges to PN intervention implementation through a weekly written report. [name], a licensed psychologist, and [name] will also provide the patient navigators with weekly, and as needed clinical supervision.

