### 7.2 SAMPLE SIZE DETERMINATION

For the open pilot, N = 30 was selected based on recommendations in the field which specify 15 to 30 participants per condition are satisfactory for pilot trials. Given the open pilot includes a single condition, we planned for the upper limit sample size based on these recommendations.

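### Does the statement in Section 5.1.1 that no interventionist is shared call for an analysis of clustering by navigator?

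*Combined protocol and SAP*

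**What the plan says.** All references are to the combined protocol and SAP.

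- **The statement at issue.** Section 5.1.1 closes its account of delivery by saying that "participants will not interact with other participants or with a shared interventionist throughout the duration of the study".
- **Who delivers.** Section 2.3.3 uses the singular: "The intervention will be implemented by a social work navigator who will be under the supervision of" two named psychologists. A few sentences later the same paragraph speaks of navigators in the plural, as does the opening of Section 5.1.1. In Section 5.2.1 a single programme manager "will provide day-to-day supervision of the patient navigators and will meet with the navigators weekly". The number of navigators, their caseloads and the way participants are assigned to them are not stated. The synopsis says that sessions are individual.
- **Role of the navigator.** Section 2.2 names as one target "decreased thwarted belongingness (e.g. through interactions with the PN" and, in the same parenthesis, through links to support groups.
- **Design and size.** "The open trial will consist of 30 sexual and gender minority participants, aged 15-29, located in San Diego". Section 7.2 explains that "N = 30 was selected based on recommendations in the field which specify 15 to 30 participants per condition". Section 3.1 adds: "Therefore, no randomization or control group will be used".
- **Analysis.** Section 7.4.2 reports within-person change in the two targets as Cohen's d. It calls this testing, but Section 7.4.1 rules out inferential tests. Section 7 mentions no confidence interval, significance level, power figure or navigator term.

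**The concern.** Individual sessions keep participants from meeting one another. They do not stop two participants from having the same navigator. Unless there are as many navigators as participants, the second half of the sentence is untrue, and a reader who relied on it would conclude that navigator effects cannot arise.

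That could matter more here than in many pilots, because the relationship with the navigator is one of the proposed routes to lower thwarted belongingness. Participants of the same navigator may therefore change in similar ways. Treating 30 changes as independent would then overstate how precisely d describes PN+SPI in other hands. With a single navigator, the effect of the person and the effect of the programme could not be told apart at all. A later randomised comparison might be planned from a pilot that appears to deny this source of variation.

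**Working it through.** **1. The plan's own figure.** There is no power calculation to reproduce. N = 30 is the upper end of a rule of thumb for one condition (30 × 1 = 30). It agrees with the accrual of "five participants per month over six months" (5 × 6 = 30).

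**2. Is sharing likely?** The minimum schedule in Section 5.1.1 is a first session, seven weekly contacts, then monthly contacts to about day 183. The monthly part lasts (183 − 1 − 49)/30.4 = 4.4 months, so four contacts. That gives 1 + 7 + 4 = 12 contacts per participant and 30 × 12 = 360 in all. Thirty separately hired and trained navigators for that workload is implausible, so sharing is a fair inference. It remains an inference, because no number is given.

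**3. Size if outcomes cluster.** Both inputs are assumptions: K navigators with equal caseloads m = 30/K, and an ICC. Design effect = 1 + (m − 1) × ICC. Effective N = 30/design effect. The 95% half-width of the mean change, in SDs of change, is 1.96 × √(design effect/30). With no clustering it is 1.96 × √(1/30) = 0.358.

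| K | m | ICC | Design effect | Effective N | Half-width |
|---|---|---|---|---|---|
| 2 | 15 | 0.01 | 1.14 | 26.3 | 0.382 |
| 2 | 15 | 0.05 | 1.70 | 17.6 | 0.467 |
| 2 | 15 | 0.10 | 2.40 | 12.5 | 0.554 |
| 3 | 10 | 0.01 | 1.09 | 27.5 | 0.374 |
| 3 | 10 | 0.05 | 1.45 | 20.7 | 0.431 |
| 3 | 10 | 0.10 | 1.90 | 15.8 | 0.493 |
| 5 | 6 | 0.05 | 1.25 | 24.0 | 0.400 |

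The answer runs from a minor loss to more than half the information, depending wholly on inputs the documents do not supply. With K = 1 the ICC cannot be estimated.

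**4. What the planned result uses.** Cohen's d is a mean change divided by an SD. Neither step involves a standard error, so nothing in the last column enters a planned result.

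**5. Would a table by navigator help?** Take two navigators with 15 participants each and a total SD of change of 1. At ICC 0.05:
- The true difference between two navigators has SD √(2 × 0.05) = 0.32.
- Sampling error in the observed difference is √(2 × 0.95/15) = 0.36.
- The share of the observed variance that is real is 0.100/(0.100 + 0.127) = 44%.

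At ICC 0.01 the share is 0.020/(0.020 + 0.132) = 13%. At 0.10 it is 0.200/(0.200 + 0.120) = 63%. In every case this is a single contrast between two people.

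**6. Would an inflated interval help?** The half-widths above treat the ICC as known. If between-navigator variation had to be learned from two navigators, there would be one degree of freedom and a multiplier of about 12.7 in place of 1.96. At ICC 0.05 the half-width would be 12.7 × √(1.70/30) = 3.0 SD. The inflated interval of ±0.467 would look far more certain than the data allow, and the honest interval would say nothing.

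**The case for a change.** The strongest case for a change is that the sentence in 5.1.1 makes a positive claim that the rest of the document does not support. Its first half already covers contact between participants, so the second half cannot simply be a restatement that sessions are individual. Effect sizes are the stated outcome of interest and precede a possible randomised phase. Recording who treated whom would cost one variable, and it may be hard to recover later. Because the plan is descriptive, a descriptive remedy would suit it.

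Much of this stands. The sentence is wrong as written if any navigator sees two participants, and d will be specific to the navigators used. But the singular in Section 2.3.3 is weak evidence of a single navigator when the same paragraph turns to the plural. That outcomes are in fact clustered is not shown. Navigators complete the encounter records themselves, and the listed items follow the word including, so the absence of navigator identity from the list does not show that it goes unrecorded. Section 8.1.7 also leaves operating detail to a Manual of Procedures. Delivery variation is addressed in part by manual-based training, checklist coding of recordings, weekly supervision and a scale of satisfaction with the navigator relationship. Nothing in the documents says that a later trial would take its variance or sample size from this d.

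**Conclusion.** No change to the plan is needed. The wording of 5.1.1 conflicts with the delivery described elsewhere, most likely as a slip meant to convey one-to-one delivery, and no planned result depends on it. The number of navigators and their caseloads are missing details that any competent report of the open trial would give, together with the remark that d describes these navigators. With one navigator, person and programme are inseparable and no analysis could change that. The trial also has no control arm, so its change could not be credited to PN+SPI alone even with many navigators.

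The effective sample sizes (26.3 to 12.5 with two navigators, 27.5 to 15.8 with three) illustrate assumed ICCs of 0.01 to 0.10. They invalidate no test, interval or power statement, because the plan contains none. This conclusion rests on the analysis staying descriptive. If the authors chose to publish an interval for d, they should say that it ignores variation between navigators.

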### 5.2 FIDELITY

#### 5.2.1 INTERVENTIONIST TRAINING AND TRACKING

The patient navigators, who will be social workers, will be extensively trained (e.g., through didactics and role playing) by the study team using training manuals developed in collaboration

with the PPG and via the Patient Navigation Research Program (PNRP) training approach. Patient navigators will be trained on all SOPs that are relevant to their work (i.e., child and elder and dependent adult abuse and neglect) and will have significant training in safety monitoring. This training will include didactic approaches as well as active learning, such as role playing with the investigative team and community members. General PN training will focus on the history of PN, establishing rapport, professionalism in PN, and documenting the PN services provided. In addition, more specific training will be provided in how to administer the SPI content of the integrated intervention, as well as the 7 PN intervention modules, one of which includes addressing suicidal crises. Based on prior PN studies, it is anticipated that training will last at least 2-3 weeks to allow the patient navigators adequate time to practice delivering intervention modules, documenting care provided, and following study data collection protocols. However, training may be extended depending on each navigator's needs. All staff who will be interacting with participants will be trained in the techniques of the UWRAP as it pertains to their role in the project.

Intervention fidelity will be assessed via audio-recordings and observation conducted by the study project director. Audio-recordings, considered the gold standard in treatment fidelity, will be evaluated by the trained project director who will code the recordings using a checklist to track whether the interventionists delivered PN+SPI according to the manual. Using an approach developed by the PNRP, patient navigators will record process data related to the PN services provided, including: 1) number of encounters, 2) length of time of each encounter; 3) barriers experienced by patients; and 4) actions taken to reduce barriers. Patient navigators will keep copies of the participants' safety plans and the SPI suicide risk curve. The patient navigators will also be asked to keep detailed qualitative notes regarding telephone, text, and in-person encounters with participants, including participants' progress in obtaining mental health services, successes in implementing the PN intervention, and challenges in implementing the PN intervention. A Research Program Manager at FHCSD will provide day-to-day supervision of the patient navigators and will meet with the navigators weekly and document successes and challenges to PN intervention implementation through a weekly written report. [name], a licensed psychologist, and [name] will also provide the patient navigators with weekly, and as needed clinical supervision.

